6.0 TREATMENT AND EVALUATION OF ENDPOINTS

6.1 Baseline Visit

6.1.1 Clinical Assessments

The items listed below will be collected from each subject at the Baseline Visit. Information gathered at this visit may be used to verify eligibility of the subject for the trial.

- Documentation of the informed consent process
- Confirmation of enrollment criteria, including pregnancy test if patient is a female of child bearing potential
- Subject demographics
- Complete physical exam including height, weight, and NYHA assessment (If these assessments were performed prior to consent, they may be used if they were completed within 60-days of the ablation procedure)
- Cardiovascular disease history (most recent value prior to baseline visit)
- Arrhythmia history including documentation of AF (including paroxysmal or persistent)
- Antiarrhythmic medication – including any current class I/III AAD and dose, and history of any class I/III AAD and maximum dose
- Current anticoagulant medication

Clinical Investigation Plan

Record the required information on the appropriate CRFs. Any protocol deviations (refer to Section 10.5 for details) observed will also be recorded at this time.

6.1.2 Patient Reported Outcome Measures

The EQ-5D-5L²² Questionnaire is a widely used validated questionnaire used to measure quality of life. The self-administered/electronic questionnaire consists of 6 questions. The subject is instructed to choose the option that best describes their health on the day of the assessment. The questionnaire takes approximately 5 minutes to complete.

The Site Coordinator or designee will administer the EQ-5D-5L patient-reported outcome (PRO) questionnaire. It is important the subject understands the meaning of all words and instructions in the questionnaire. The subject should be instructed to ask any questions about the questionnaire if further explanation is needed. Once the questionnaire is completed, the Site Coordinator or designee will review for completeness to verify that all questions have been answered according to the directions provided.

6.2 Index Procedure

The procedure should be performed according to the IFU/Package Insert of the specific HD mapping catheter, EnSite Cardiac Mapping System, and any other medical devices used during the procedure. Physicians performing electroanatomical mapping and ablations must be qualified operators and trained on the study. Each physician who ablates during a particular case needs to be documented on the Procedure CRF.

The following information will be collected during the Procedure Visit:

- Antiarrhythmic medications - any current class I/III AAD and dose
- Anticoagulant medications
- Subject cardiac rhythm when they enter the EP lab
- Subject cardiac rhythm during mapping
- Mapping and ablation tools used during the procedure
- Procedural characteristics (set up and timing)
- Fluoroscopy time
- Mapping time (total time to collect mapping data and time for each map created/retrospectively generated)
- Mapping points collected and used for each map created/retrospectively generated
- Mapping location(s)
- Electrode configuration used for clinical electroanatomical mapping
- Map type(s) (i.e. Voltage, LAT, CFE, etc.)
- AutoMap settings used (if applicable)
- Arrhythmogenic substrate identified
- Field Scaling use
- Ablation strategy
- AutoMark settings used (if applicable)
- Cardioversions performed during procedure
- Attempt(s) at induction of arrhythmia as applicable before and after RF delivery
- Subject rhythm after completion of procedure

Clinical Investigation Plan

Protocol deviations (refer to Section 10.6 for details) and Adverse Events (refer to Section 7.0) that were observed during the procedure, which include any device used off-label during the procedure, will also be recorded at this time.

6.2.1 Pre-procedure thrombus assessment

Thrombus assessment is required before procedure and will be performed per investigator's standard of care. If a thrombus is discovered, the procedure should be postponed and the subject placed on anticoagulation until the thrombus is resolved and confirmed by imaging. The subject may be re-consented for the study if the thrombus resolves within 90 days of detection. Baseline visit information will be verified and updated as necessary.

6.2.2 General procedural recommendations

Create a baseline geometry and map (at a minimum, collect baseline voltage map, other maps may be collected per standard of care) of the atrium using the HD mapping catheter of choice per IFU/Package Insert. Create and/or retrospectively generate the desired electroanatomical maps. Use these maps as clinically necessary to identify ablation target(s). Use ablation catheter per IFU/Package Insert to perform ablation per standard of care. Assess acute procedural success. Create post-ablation voltage map or collect additional maps and perform additional ablation if clinically necessary. Ablation to treat other arrhythmias that occur during the procedure are allowed per physician discretion and standard of care.

6.2.3 Electroanatomical mapping

The HD Mapping catheters must be used with the EnSite Cardiac Mapping System and the EnSite Automap module to generate a baseline electroanatomical map prior to the ablation procedure. Complete contact with the cardiac wall should be achieved before collecting data. Mapping will be done per investigator discretion and SOC for the particular study site. When using the HD Grid mapping catheter, it is recommended to use an HD Wave electrode configuration for catheter set-up (see Appendix X).

6.2.4 Indication Specific recommendations

If the subject presents in atypical AFL at any time during the procedure or as a result of induction, diagnostic mapping and RF ablation will be allowed. Details pertaining to the ablation of atypical AFL should be recorded in the corresponding CRF.

6.3 Pre-discharge Visit (In-hospital)

6.3.1 Clinical Assessments

Prior to discharge after the study procedure, a Pre-discharge visit will be completed. The following information will be collected from each subject:

- Arrhythmia recurrence
 - For the purposes of this clinical study recurrence of arrhythmia is deemed to have occurred only when the arrhythmia is documented on ECG, or other monitoring device used per standard of care. Atrial arrhythmias 30 seconds or longer will be collected.
- Antiarrhythmic medications - any current class I/III AAD and dose
- Adverse events if applicable
- Protocol deviations if applicable

Clinical Investigation Plan

6.4 Follow-up Visits

6.4.1 Clinical Assessments

A Follow-up visit will be scheduled at 6 months (180 days \pm 14 days) and 12 months (360 days \pm 14 days) post procedure. The scheduled visit windows are calculated from the index procedure. The visit must be completed in-clinic. The following information will be collected:

- Arrhythmia recurrence
- Antiarrhythmic medications - including any current class I/III AAD and dose
- Other monitoring device source documentation of arrhythmia if applicable
- Adverse events if applicable
- Protocol deviations if applicable
- 24-hour Holter monitor (at 12-month visit only)
 - A core laboratory will review each recording and report findings to the Sponsor.

Note: The Sponsor may request access to other patient data during the required protocol follow up visits or throughout the follow up period, which may include, but is not limited to, data from implanted device(s). Record the required information on the appropriate CRF(s). Documentation of arrhythmia (e.g. ECG printouts and/or Holter reports) where applicable, should be retrieved and submitted electronically through EDC to the Sponsor.

Sponsor representatives can be involved in providing support during the follow-up procedures.

6.4.2 Patient Reported Outcomes

The Site Coordinator or designee will administer the EQ-5D-5L questionnaire at both the 6-month and the 12-month visit. It is important the subject understands the meaning of all words and instructions in the questionnaire. The subject should be instructed to ask any questions about the questionnaire if further explanation is needed. Once the questionnaire has been completed, the Site Coordinator or designee will review for completeness to verify that all questions have been answered according to the directions provided.

6.5 Unscheduled Visits

6.5.1 Clinical Assessments

If a subject is seen by any physician for possible arrhythmia recurrence and/or arrhythmia associated symptoms outside of a regularly scheduled study visit and/or had an urgent care or emergency room visit regarding possible arrhythmia, these visits need to be documented as "Unscheduled Visits". Minimally, the following information should be documented for an unscheduled visit:

- Monitoring device source documentation of arrhythmia if applicable
- Antiarrhythmic medication - including any current class I/III AAD and dose
- Occurrence of any repeat ablation
- Document adverse events if applicable
- Protocol deviations if applicable

Clinical Investigation Plan

6.5.2 Patient Reported Outcomes

As performed during the baseline visit, the Site Coordinator or designee will administer EQ-5D-5L questionnaire. It is important the subject understands the meaning of all words and instructions in the questionnaire. The subject should be instructed to ask any questions about the questionnaire if further explanation is needed. Once the questionnaire is completed, the Site Coordinator or designee will review for completeness to verify that all questions have been answered according to the directions provided.

6.6 Schedule of Events

The schedule of activities specific to this clinical study are described in the preceding sections and are summarized in Table 2.

Table 2. Clinical Study Specific Tests/Activities and Procedures

CIP Activity	Baseline	Procedure	Pre-Discharge	6 Month (180 days ± 14 days post procedure)	12 Month (360 days ± 14 days post procedure)	Unscheduled Visit
Informed Consent Process	X					
Eligibility Check	X	(X)				
Demographics	X					
Physical Examination	X					
Cardiovascular Disease History	X					
Arrhythmia History	X					
Anticoagulant Medication	X	X				
Antiarrhythmic Medication	X	X	X	X	X	(X)
Mapping of cardiac structures and electroanatomical map(s)		X				
RF Ablation		X				
EQ-5D-5L PRO Questionnaire	X			X	X	X
24-hour Holter-monitoring					X	(X) ^a
Other arrhythmia monitoring and source documentation			(X)	(X)	(X)	(X)
Repeat Ablation			(X)	(X)	(X)	(X)
Protocol Deviation	(X)	(X)	(X)	(X)	(X)	
Withdrawal	(X)	(X)	(X)	(X)	(X)	(X)
Adverse Events	(X)	(X)	(X)	(X)	(X)	(X)

(X) if applicable

^a Holter monitoring during an unscheduled visit does not need to be conducted through the core laboratory

6.7 Core Laboratory

A core lab will be used for the collection, interpretation, and collation of data collected from Holter monitoring.

The core lab will provide independent review of this data by appropriately trained personnel using standardized procedures to interpret Holter monitor tracings for adjudication of atrial arrhythmias. Findings will be communicated to the investigator and to Abbott. The core lab's adjudication findings will be used for analysis.

Clinical Investigation Plan

7.0 Adverse Events

To comply with worldwide standards and guidelines on clinical investigation adverse event reporting, the Sponsor has adopted uniform and worldwide applicable standard definitions and reporting timelines to be used and adhered to by the investigators.

7.1 Definition

7.1.1 Adverse Event

An adverse event (AE) is any untoward medical occurrence, unintended disease or injury, or untoward clinical signs (including abnormal laboratory findings) in subjects, users or other persons, whether or not related to the medical device under investigation.

Note 1: This definition includes events related to the medical device under investigation or the comparator.

Note 2: This definition includes events related to the procedures involved.

Note 3: For users or other persons, this definition is restricted to events related to medical devices under investigation.

7.1.2 Serious Adverse Event

If the AE meets any of the criteria below, it is regarded as a serious adverse event (SAE).

- Led to a death,
- Led to a serious deterioration in health of the subject, that either resulted in
 - a life-threatening illness or injury, or
 - a permanent impairment of a body structure or a body function, or
 - in-patient hospitalization or prolongation of existing hospitalization, or
 - medical or surgical intervention to prevent life threatening illness or injury or permanent impairment to a body structure or a body function.
 - chronic disease
- Led to fetal distress, fetal death or a congenital abnormality or birth defect.

Note: A planned hospitalization for pre-existing condition, or a procedure required by the CIP, without a serious deterioration in health, is not considered to be an SAE.

7.2 Device Relationship

Determination of whether there is a reasonable possibility that an investigational product or device under investigation caused or contributed to an AE is to be **determined by the Investigator** and recorded on the appropriate CRF form. Determination should be based on assessment of temporal relationships, evidence of alternative etiology, medical/biologic plausibility, and patient condition (pre-existing condition).

7.3 Adverse Event Reporting

7.3.1 Adverse Event Reporting

Safety surveillance and reporting starts as soon as the patient is enrolled in the clinical investigation. Safety surveillance and reporting will continue until the last follow-up visit has been performed, the subject is deceased, the subject concludes participation in the clinical investigation or the subject

Clinical Investigation Plan

withdraws from the clinical investigation. Adverse event data, including deaths, will be collected throughout the time period defined above and will be reported to the Sponsor on a CRF. Additional information with regard to an adverse event should be updated within the appropriate CRF.

Unchanged, chronic, non-worsening or pre-existing conditions are not AEs and should not be reported.

An offline form will be made available to allow the investigator to report serious adverse events (SAEs) in the event the entry cannot be made in the EDC. This does not replace the EDC reporting system. All information must still be entered in the EDC system as soon as feasible.

Non-cardiac related abnormal laboratory values will not be considered AEs unless:

1. the investigator determined that the value is clinically significant,
2. the abnormal lab value required intervention, or
3. the abnormal lab value required subject withdrawal from the clinical investigation.

For the purposes of this clinical investigation, the following events will be reported:

- Adverse events that are considered related to either the ablation catheter or the ablation procedure by the investigator
- Adverse events resulting in death

Recurrence of AF, AFL, or AT are not considered reportable adverse events unless they occur in a severity, frequency, or other manner that is significantly worse than the subject's baseline condition. These are considered lack of effectiveness and will be reported as a recurrence on the appropriate case report form.

SAE Reporting

The investigator should report all SAEs to the Sponsor as soon as possible but no later than outlined below.

Clinical Site	Reporting timelines
All Sites	SAEs must be reported to the Sponsor no later than 3 calendar days from the day the site personnel became aware of the event or as per the investigative site's local requirements, if the requirement is more stringent than those outlined.

The date the site staff became aware the event met the criteria of an SAE must be recorded in the source document. The Investigator will further report the SAE to the local IRB/EC according to the institution's IRB/EC reporting requirements.

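### As worded, Section 7.3.1 can exclude a pre-existing condition that worsens after the procedure from both AE and SAE reporting, in conflict with 7.1.1 and 7.1.2

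*Combined protocol and SAP*

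**What the plan says.** Section 7.3.1 (Adverse Event Reporting) contains the exemption: "Unchanged, chronic, non-worsening or pre-existing conditions are not AEs and should not be reported". It then names what is to be reported: AEs that the investigator relates to the ablation catheter or procedure, and AEs that end in death. All SAEs must go to the sponsor within a set time. For recurrence of AF, AFL or AT the section has a separate rule: recurrence is not reportable "unless they occur in a severity, frequency, or other manner that is significantly worse than" the subject's baseline state.

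Section 7.1.1 defines the AE broadly: "An adverse event (AE) is any untoward medical occurrence, unintended disease or injury, or untoward clinical signs (including abnormal laboratory findings) in subjects". Its second note adds: "This definition includes events related to the procedures involved".

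Section 7.1.2 builds the SAE on the AE: "If the AE meets any of the criteria below, it is regarded as a serious adverse event (SAE"). One criterion is "Led to a serious deterioration in health of the subject, that either resulted in" any of several outcomes, and the outcomes listed include permanent impairment and "chronic disease". A closing note leaves out planned admissions for a pre-existing condition, but only where the subject's health has not seriously deteriorated.

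**The concern.** The exemption does more than remove a reporting duty. It says that the listed conditions are not AEs at all. If a site takes *pre-existing* as a sufficient reason, a baseline disease made worse by the procedure never enters the safety data.

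Adverse events are the harms evaluation in Section 4.3, and Section 8.2.2 plans tables of cardiovascular SAEs. Heart failure is a natural example. NYHA class and cardiovascular history are recorded at baseline (6.1.1), but Table 2 repeats neither the history nor the physical examination that includes NYHA class. At 6 and 12 months the AE form is therefore the main place where a clinician would record such a worsening. With up to 20 sites (3.0), some could follow the wording and others its likely intent. The harms result would then be too low at some sites and would differ between sites for reasons unrelated to patients.

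**Working it through.** The plan states no figure on this point, so the check is a reading of the sections against one another.

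1. **The exemption itself (7.3.1).** Four terms are joined by *or*. Two describe stability (unchanged, non-worsening) and two describe type (chronic, pre-existing). Grammatically, any one term is enough. A pre-existing disease that worsens is still pre-existing, so it satisfies the sentence, and no *unless worsened* clause follows.

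2. **Against the AE definition (7.1.1).** An AE is "any untoward medical occurrence, unintended disease or injury", among other things, and procedure-related events are included. Worsening of a disease by the procedure fits this definition. Sections 7.1.1 and 7.3.1 therefore give opposite answers for the same event.

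3. **Whether SAE reporting rescues the case (7.1.2).** The SAE test is applied to an AE. If 7.3.1 has already removed AE status, the test is never reached. The duty to report all SAEs then adds nothing.

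4. **Whether the list of reportable events rescues it (7.3.1).** Each item on that list also begins from an adverse event, so the same step blocks it. A death would still surface as a reason for discontinuation under 5.5. The exposure is therefore mainly to non-fatal worsening.

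5. **Against the SAE criteria (7.1.2).** Serious deterioration is a criterion, and chronic disease is one of its listed outcomes. The note on planned admissions protects a pre-existing condition only when there is no such deterioration. Section 7.1.2 thus treats worsening as in scope, while the wording of 7.3.1 can put it out of scope.

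6. **How 7.3.1 writes exceptions elsewhere.** Both the rule on non-cardiac laboratory values and the rule on arrhythmia recurrence carry an explicit *unless*. The sentence on chronic and pre-existing conditions has none.

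7. **New lasting injury.** It is neither pre-existing nor unchanged, it meets 7.1.1, and it can be serious under 7.1.2. Only the word *chronic* points the other way.

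**Size.** No rate of procedure-related worsening appears in the documents, so no count of missed events can be derived. For scale only: with about 200 subjects (3.0), each affected subject left out lowers a reported proportion by 1/200 = 0.5 percentage points, if all 200 are in the denominator.

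**The case against.** The best reply is that the sentence is a loose description of stable baseline disease. If *pre-existing* and *chronic* were each sufficient, *unchanged* and *non-worsening* would add almost nothing for baseline disease. Taken alone, *non-worsening* would exempt any new injury that had stabilised, which nobody can intend. The rest of Section 7 also treats worsening as in scope: the note in 7.1.2, the duty to report procedure-related AEs, the worse-than-baseline rule for recurrence, and the mention of pre-existing condition in 7.2 as something to weigh when judging causality. The recurrence rule has its own reason to exist, since recurrence is an effectiveness outcome with its own form. Its presence does not prove that other worsening was meant to be exempt. Sites are trained on the protocol and on CRF completion (10.4.1), and the CRFs, which are held separately, may already clarify the point.

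Most of this stands as evidence of intent, but it does not repair the sentence. If stable conditions are meant, the conjunction says something else. Training and central data review (10.5) are described without reference to this rule, and central review has difficulty finding an event that was never entered.

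A reader might infer two stronger things. One is that a new lasting injury need not be reported. The documents do not support that: such an injury is an AE when it occurs, and lasting does not undo that status. The other is that a stated share of the study's harms depends on this sentence. That would need event rates the documents do not contain.

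**Conclusion.** The point holds in a limited form. Section 7.3.1 states a reporting rule that, as written, can exclude a worsened pre-existing condition from AE status and so from procedure-related AE and SAE reporting. It conflicts with 7.1.1 and 7.1.2. For new lasting injury there is only an inconsistency in the word *chronic*, not an exemption.

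The plan does not appear to intend that worsening go unreported, and nothing in the documents shows that any site will read it that way. The conclusion rests on the wording alone, and on the CRF instructions, which could not be seen, not already settling the matter. The size of any under-reporting is unknown. The change should be made because the defect affects the study's harms evaluation and is easy to correct.

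**What to change.** Reconcile 7.3.1 with 7.1.1 and 7.1.2 by replacing the sentence with wording such as: *Chronic or pre-existing conditions that are unchanged and not worsening since enrolment are not AEs. Any condition that is new or has worsened since enrolment is assessed under Sections 7.1.1 and 7.1.2 and reported under the rules of this section.* The existing rule on AF, AFL and AT recurrence can stay as it is. Repeat the wording in the AE CRF instructions so that all sites apply one rule.

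The cost is one protocol sentence and the matching CRF guidance. Treatment, endpoints and sample size do not change. The reported AE count may rise slightly.

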2.2.2 Indication for Use

Indications for use may be found in the appropriate device IFU/Package Insert. Indications for the use of each of the HD mapping catheters and the specific EnSite Cardiac Mapping System are described below.

The Advisor™ HD Grid Mapping Catheter, Sensor Enabled™, is indicated for multiple electrode electrophysiological mapping of cardiac structures in the heart with recording or stimulation only. This catheter is intended to obtain electrograms in the atrial and ventricular regions of the heart.

The Inquiry™ AFocus™ catheters are for recording intracardiac signals and cardiac stimulation during diagnostic electrophysiological studies. The Inquiry™ AFocus™ catheters are for use in mapping atrial regions of the heart.

The EnSite Velocity™ Cardiac Mapping System is a catheter navigation and mapping system capable of displaying the three-dimensional (3D) position of conventional electrophysiology catheters, as well as displaying cardiac electrical activity as waveform traces and as dynamic 3-D isopotential maps of the cardiac chamber. The contoured surfaces of these three-dimensional maps are based on the anatomy of the patient’s own cardiac chamber. The EnSite Velocity™ Cardiac Mapping System (including AutoMap) is a suggested diagnostic tool in patients for whom electrophysiology studies have been indicated. When

Clinical Investigation Plan

used with an EnSite Velocity™ Surface Electrode Kit, the EnSite Velocity™ Cardiac Mapping System is intended to display the position of conventional electrophysiology (EP) catheters in the heart.

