3.1 Clinical Investigation Procedures and Follow-up Schedule

Subjects will be consented for the trial prior to any data collection. Once eligibility is confirmed and a subject is consented, baseline information will be collected and the subject will undergo the RF ablation procedure per physician discretion using electroanatomical mapping with either Inquiry™ AFocusII™ Double Loop or Advisor™ HD Grid, Sensor Enabled™ depending on market release in the specific region. Subjects will be followed for 12 months post procedure. Follow-up assessments will occur in person at a clinic. The study visits will occur at baseline, procedure, pre-discharge, 6 months post ablation procedure, and 12 months post ablation procedure. The subject will be exited from the study after completion of the 12-month follow-up visit. The visit schedule and related study assessments are summarized in Figure 4 and further detail is provided in Section 6.0.

Clinical Investigation Plan

[figure not shown]

Figure 3. Clinical Investigation Flow Chart

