4.3 Additional Evaluations

- Adverse events including any device-, procedure-, or death-related events.
- Rate of repeat ablations after study procedure during 12-month follow up defined as proportion of subjects with an additional ablation procedure to treat indicated cardiac arrhythmia (outside blanking period, if applicable).
- Change in quality of life (QOL) at 6 months and 12 months after receiving HD mapping and RF ablation relative to baseline: defined as change in quality of life assessed in the validated EQ-5D-5L QOL survey.

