APPENDIX XII: CIP SUMMARY

Clinical Investigation Name and Number	HD Mapping Observational Study (CRD_975)
Objective(s)	The aim of this study is to quantify and characterize the outcomes of radiofrequency (RF) ablation after, and the utility of, electroanatomical mapping with to characterize the utility and outcomes of electroanatomical mapping with the market-released HD mapping catheters Inquiry™ AFocusII™ Double Loop and Advisor™ HD Grid, Sensor Enabled™ with the EnSite Cardiac Mapping System and Automap module in subjects with AF in the real-world environment of the Asian Population.
Device Under Investigation	
 • Inquiry™ AFocusII™ Double Loop EP Catheter • Advisor™ HD Grid Mapping Catheter, Sensor Enabled™ (HD Grid) • EnSite Cardiac Mapping System 
 ○ EnSite Precision™, SV 2.2 or higher OR ○ EnSite Velocity™, SV 5.0 or higher (China only)
Number of Subjects Required for Inclusion in Clinical Investigation	Approximately 200 subjects will be enrolled in this study.
Clinical Investigation Design	Prospective, non-randomized, multi-center, single-arm, post-market observational
Endpoints	
Utility Endpoint
 
The utility of HD Mapping catheters with the EnSite Cardiac Mapping System will be quantified and characterized through the summary of the following:
 
 • Overall procedure time: defined as time from initial catheter insertion to final catheter removal. • Radiofrequency (RF) time: defined as duration of time RF energy is delivered • Fluoroscopy time: defined as total time subject is exposed to fluoroscopy • Mapping time associated with mapping arrhythmia: defined as the total cumulative mapping time and mapping time for the creation of each map (including any new or retrospective map created with Manual, AutoMap, and TurboMap mapping) • Number of mapping points collected: defined as total number of mapping points collected for the creation of each map • Number of mapping points used: defined as the total number of mapping points used in each map • Number of used mapping points per minute: defined as the total number of mapping points used divided by the relative mapping time

Clinical Investigation Plan

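### The reportable-event list in section 7.3.1 names the ablation catheter and procedure but none of the devices under investigation, so non-serious events tied only to mapping may go unreported

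*Combined protocol and SAP*

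**What the plan says.** Section 7.3.1 carries three statements on scope.

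- A general sentence with no limit by cause: "Adverse event data, including deaths, will be collected throughout the time period defined above and will be reported to the Sponsor on a CRF".
- A two-item list of what is reported in this study. One item is "Adverse events that are considered related to either the ablation catheter or the ablation procedure by the investigator"; the other is any adverse event with a fatal outcome.
- A rule for serious events with no relatedness condition: "The investigator should report all SAEs to the Sponsor as soon as possible but no later than outlined below".

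The section does not say how the three fit together.

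Other sections set the scope by the study devices. Section 4.3 promises an evaluation described as "Adverse events including any device-, procedure-, or death-related events". Note 1 of section 7.1.1 puts events related to the device under investigation inside the definition of an adverse event, and Note 2 does the same for the procedures involved. Section 7.2 asks the investigator for a "Determination of whether there is a reasonable possibility that an investigational product or device under investigation caused or contributed to an AE", recorded on a CRF.

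The CIP summary in Appendix XII gives the devices under investigation as the AFocusII catheter, the HD Grid catheter and the EnSite Cardiac Mapping System. Neither that entry nor Table 1 in section 2.2.1 contains an ablation catheter.

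**The concern.** The study exists to characterise mapping devices, yet the device half of the reporting list points to an ablation catheter, which is not among the study devices. A site that treats the list as its instruction could reasonably leave out a non-serious event that it attributes to a mapping catheter, to EnSite or to mapping itself. Another site, working from the general collection sentence or from section 4.3, would report the same event. With up to 20 sites (section 3.0), the device-related evaluation in 4.3 could then be incomplete or uneven for this class of event, and events never entered may not be recoverable at analysis.

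**Working it through.** The plan states no figure on this point and no arithmetic applies. The check has three steps.

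**1. Can the device half of the bullet be read to include the study devices?** No. Section 2.2.2 says that HD Grid "is indicated for multiple electrode electrophysiological mapping of cardiac structures in the heart with recording or stimulation only", and it describes the AFocus catheters as tools for recording and stimulation in diagnostic studies. Neither is an ablation catheter, and EnSite is a navigation and mapping system. Of the three devices under investigation in Appendix XII, the list names none.

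**2. Can the procedure half be read to include mapping?** Possibly. Section 3.1 supports that reading: "the subject will undergo the RF ablation procedure per physician discretion using electroanatomical mapping" makes mapping part of the ablation procedure. Two other places treat them as distinct. Section 6.2.3 puts the baseline map ahead of the ablation procedure, and section 8.1 defines the analysis population by a mapping procedure and, as a further condition, receipt of RF ablation. The wording does not settle the question.

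**3. Which events are covered by the list and the SAE rule?**

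- Fatal, any attribution: covered by the second item of the list.
- Serious, attributed only to a mapping device or mapping: covered by the SAE rule.
- Non-serious, attributed to the ablation catheter or ablation procedure: covered by the first item.
- Non-serious, attributed only to a mapping catheter, EnSite or mapping: not named. It comes in only if ablation procedure means the whole session, or if the general collection sentence prevails. It is nevertheless within sections 4.3, 7.1.1 and 7.2.

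Only the last class is exposed. The gap is easiest to see in a subject whose session ends after mapping. Section 5.4 makes insertion of the HD mapping catheter the last step of enrolment, and 7.3.1 starts safety reporting at enrolment. A non-serious event from the mapping catheter would then fall in the reporting period with no ablation to attribute it to. Section 8.1 limits the endpoint population to subjects who received RF ablation, so this example bears on reporting more than on endpoint analysis.

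The complaint route in 7.3.3 does not close the gap, because complaint information is kept off the study CRFs.

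**The case against.** The best reply is that the protocol already has wider routes of capture. The general sentence in 7.3.1 has no limit by cause, and nothing says that the list narrows it. Section 6.2 has adverse events seen during the procedure recorded, and that procedure includes mapping; it refers to section 7.0 as a whole, which takes in the broad definition in 7.1.1. Sections 6.3 to 6.5 and Table 2 ask for adverse events at the later visits. Sections 6.2.3 and 8.1 describe sequence and population, not adverse event scope. Sponsor training (10.4.1) and central data review (10.5) could also bring sites to one reading.

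Much of this stands, and it is why loss of data can only be called possible. It does not remove the conflict: a list introduced as the events to be reported still omits the study devices, and the section does not say what the list is for if everything is collected anyway.

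A reader might infer that mapping-related safety data will not be collected at all. The documents do not support that, given the SAE rule, the item on deaths and the broader routes above. A reader might also take section 15.2 as separating diagnostic from ablation procedures for attribution. It does not: it compares the study's risks with those of other commercially available procedures, then speaks of a single procedure.

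**Conclusion.** The inconsistency is real and should be fixed. Its reach is narrow: non-serious events attributed only to a mapping catheter, EnSite or mapping. For these, the evaluation in 4.3 may be incomplete or depend on how each site reads the section.

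The size cannot be stated, because the documents give no expected rate of mapping-related events. The only safety tables named in the visible text of section 8.2.2 concern cardiovascular serious events, which the SAE rule supplies. The study is descriptive, with no hypothesis tests (8.0) and no pass/fail criteria (8.10), so no decision rule is affected.

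The conclusion rests on the visible text. The CRFs are under separate cover (Appendix VII), the table mockups are not available, and parts of section 8 are redacted. Section 8.2.2 refers to pre-defined adverse events and a safety analysis population that the visible text does not define. Any of these might show wider capture in practice. They would not change the mismatch between 7.3.1 and sections 4.3, 7.1.1 and 7.2.

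**What to change.** Reconcile section 7.3.1 with sections 4.3, 7.1.1 and 7.2 and with Appendix XII.

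- Extend the first item of the list to adverse events that the investigator considers related to the HD mapping catheter, the EnSite system or the mapping procedure, as well as to the ablation catheter or the ablation procedure.
- State that the duty to report all SAEs is in addition to the list.
- Do not state that the list limits the general collection sentence. That sentence now has no limit by cause, and narrowing it would discard data for no stated reason.

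The cost is a short protocol amendment, with ethics committee acknowledgement or approval documented before it takes effect (section 10.3), and possibly updates to the CRFs and site training. Sites would file some additional non-serious reports, the number of which cannot be estimated from the documents.
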